12.6.1 Efficacy Endpoints and Analyses (Secondary)

Key Secondary Endpoints

- A composite of the proportion of patients with hospitalisation or death related to major complications of device implantation (i.e., need for thoracotomy, pericardiocentesis, or vascular surgery) or complications of long-term device therapy (i.e., infection not leading to hospitalisation, lead and/or generator removal/replacement, inappropriate shocks, explantation). This endpoint will be analysed for superiority. These proportions will be compared between the patients with $H/M \geq 1.60$ in the AdreView™ group and the patients with $H/M \geq 1.60$ in the SoC group, using the Cochran-Mantel-Haenszel test stratified by enrolling centre, using a 2-sided alpha value of 0.050.

- Cardiac death. The occurrence of this event will be analysed in the primary efficacy population using a Cox proportional hazards model as was performed in the primary efficacy analysis (non-inferiority [NI], using an NI margin of 1.20).
- Rate of hospitalisation for cardiovascular cause. This rate will be compared between the AdreView™ and SoC groups using the Miettinen and Nurminen methodology [\[Miettinen and Nurminen 1985\]](#), (non-inferiority [NI], using an NI margin of 1.20).
- Rate of all-cause hospitalisation. This rate will be compared between the AdreView™ and SoC groups using the Miettinen and Nurminen methodology [\[Miettinen and Nurminen 1985\]](#), (NI, using an NI margin of 1.20).
- A composite of the occurrence of resuscitated life-threatening ventricular tachycardia, unstable ventricular tachy-arrhythmias, SCD and resuscitated cardiac arrest. The occurrence of this event will be analysed in the primary efficacy population using a Cox proportional hazards model as was performed in the primary efficacy analysis (non-inferiority, using an NI margin of 1.20).

Additional Secondary Endpoints

- Syncope. The occurrence of this event will be analysed in the primary efficacy population using a Cox proportional hazards model as was performed in the primary efficacy analysis (non-inferiority, using an NI margin of 1.20).

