5 ANALYSIS CONVENTIONS

Post-text tables and listings will be prepared in accordance with the ICH M2 Guidelines [\[ICH 2008\]](#). The information and explanatory notes to be provided in the “footer” or bottom of each table and listing will include the following information:

1. Date and time of output generation;
2. SAS® program name, including the path that generates the output;
3. Any other output-specific details that require further elaboration.

In general, tables will be formatted with columns displaying findings based on the study arm for all patients. The summary tables will clearly indicate the number of patients to which the data apply and unknown or not performed are distinguished from missing data.

Supportive individual Patient Data Listings, as a minimum, will be sorted and presented by the study arm, patient number, and visit date, if applicable.

This section details general conventions to be used for the statistical analyses. The following conventions will be applied to all data presentations and analyses.

- Summary statistics for categorical variables will consist of the number and percentage of responses in each level. The number and percentage of responses will be presented in the form XX (XX.X%).
- Summary statistics for continuous variables will consist of the sample size (n), mean, median, standard deviation (SD), first quartile, third quartile, minimum, and maximum values.
- All mean, median and quartile values will be formatted to one more decimal place than the measured value. SD values will be formatted to two more decimal places than the measured value. Minimum and maximum values will be presented with the same number of decimal places as the measured value.
- All p-values, if applicable, will be rounded to 4 decimal places. All p-values that round to 0.0000 will be presented as ' <0.0001 ' and p-values that round to 1.0000 will be presented as ' >0.9999 '. Two-sided P-values < 0.05 will be considered to be statistically significant unless otherwise specified.
- All summary tables will include the analysis population sample size (i.e., number of patients).
- Study Day 1 is defined as the date at which the patient was randomised. All study days are determined relative to Day 1.
- Study days prior to Day 1 will be calculated as:
 - Study Day = Assessment Date – Randomisation Date
- Study days after Day 1 will be calculated as:
 - Study Day = Assessment Date – Randomisation Date + 1.

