- Baseline values will be defined as the last non-missing value recorded prior to randomisation.
- Change from baseline will be calculated as follows:
$$\text{Change} = \text{Post-baseline value} - \text{baseline value.}$$
- All pre- and post-enrolment assessments including unscheduled or repeat assessments will be included in the data listings.
- Date variables will be formatted as YYYY-MM-DD for presentation.

- Tables, figures, and listings will be presented in landscape orientation.
- SAS® Version 9.4 or higher will be the statistical software package used for all data analyses.

Definition of Analysis Windows

There are no visit windows for this study. For the statistical analyses, data will be analyzed by the nominal visit that was collected on the electronic case report form (eCRF).

Unscheduled visits will not be used in the by-visit analysis, but will be used for the following where appropriate: 1) derivations of baseline/last on-treatment measurements; 2) derivations of the maximum/minimum on-treatment values and maximum/minimum changes from baseline values for safety analyses; 3) data listings.

Definition of Missing Data Imputation

Missing values will not be substituted by estimated values, but treated as missing in the statistical evaluation.

Pooling of Enrolment Site

Due to the small number of patients that may have been enrolled at each study site, country will be included in the model as the stratification factor instead of the enrolment site. If there are countries that enroll only a small number of patients, the sponsor will review and provide the appropriate pooling strategy.

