5.4.2 Primary Efficacy Analysis

The primary endpoint is the hazard ratio of the all-cause mortality between the AdreView™ group and SoC. The primary efficacy endpoint will be analyzed for non-inferiority (NI) with the NI boundary equal to 1.2. If the upper bound of the confidence interval for the HR is less than 1, superiority will be claimed/ established.

The hypothesis testing for the primary objective is:

$$H_0: \text{hazard ratio (HR)} (\text{AdreView}^{\text{TM}} \text{ group} / \text{SoC}) \geq 1.2$$

$$H_a: \text{HR} (\text{AdreView}^{\text{TM}} \text{ group} / \text{SoC}) < 1.2$$

Cox proportional hazards model stratified by country, with study arm (AdreView™ group vs SoC) as the only covariate will be performed at a 1-sided alpha value of 0.025 for the primary endpoint.

Kaplan-Meier plot will be presented by method of treatment guidance. Patients who are still alive at the time of data base lock will be censored at the last known-alive date.

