5.4.3 Secondary Efficacy Analyses

5.4.3.1 Key Secondary Endpoints Analyses

- A composite of the proportion of patients with hospitalisation or death related to major complications of device implantation (i.e., need for thoracotomy, pericardiocentesis, or vascular surgery) and a composite rate of complications of long-term device therapy (i.e., infection not leading to hospitalisation, lead and/or generator removal/replacement, inappropriate shocks, explantation). This endpoint will be analysed for superiority (odds ratio of AdreView™ vs SoC < 1.0). These proportions will be compared between the patients with H/M ≥ 1.60 in the AdreView™ group and the patients with H/M ≥ 1.60 in the SoC group, using the Cochran-Mantel-Haenszel (CMH) test stratified by country, using a 2-sided alpha value of 0.05.
- Cardiac death. The occurrence of this event will be analysed using a Cox proportional hazards model as described in the primary efficacy analysis (NI, using an NI margin of 1.20). Kaplan-Meier plot will be presented by method of treatment guidance. Patients who were alive or who had died from other than cardiovascular causes at the time of data base lock will be censored at the last known-alive date.
- Rate of hospitalisation for cardiovascular cause. The odds ratio of this rate will be compared between the AdreView™ and SoC groups using the CMH test stratified by country (NI, using an NI margin of 1.20).

- Rate of all-cause hospitalisation. The odds ratio of this rate will be compared between the AdreView™ and SoC groups using the CMH test stratified by country, (NI, using an NI margin of 1.20).
- A composite of the occurrence of resuscitated life-threatening ventricular tachycardia, unstable ventricular tachy-arrhythmias, SCD and resuscitated cardiac arrest. The first occurrence of these events will be analysed using a Cox proportional hazards model as described in the primary efficacy analysis (NI, using an NI margin of 1.20). Kaplan-Meier plot will be presented by the study arm. Patients who had not experienced any of the events at the time of data base lock will be censored at the last known-alive date.

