5.4.4 Handling of Multiplicity

Due to early termination of the study by the sponsor, the sample size is not sufficient for the hierarchical hypothesis testing. All of the secondary endpoints will be analyzed inferentially as reference only.

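### For both hospitalisation endpoints the SAP sets a non-inferiority margin of 1.20 on the odds ratio but names the CMH test, whose null is OR = 1 and which therefore does not decide that hypothesis

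*SAP*

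**What the plan says.** SAP 5.4.3.1 uses the same sentence for cardiovascular and for all-cause hospitalisation: "The odds ratio of this rate will be compared between the AdreView™ and SoC groups using the CMH test stratified by country". Each bullet then labels the comparison NI with a margin of 1.20. Neither states a null hypothesis at 1.20, a significance level, a confidence level or a rule on a confidence limit.

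The other key secondary bullets in that section are more complete. The device-complication bullet also uses CMH but is a superiority comparison: "This endpoint will be analysed for superiority (odds ratio of AdreView™ vs SoC < 1.0"), at a two-sided 0.05. Cardiac death is "analysed using a Cox proportional hazards model as described in the primary efficacy analysis (NI, using an NI margin of 1.20"), and the arrhythmia composite is handled in the same way. That reference leads to SAP 5.4.2, where H0 is HR ≥ 1.2 and the Cox model "will be performed at a 1-sided alpha value of 0.025 for the primary endpoint".

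The only general convention, in SAP section 5, is: "Two-sided P-values < 0.05 will be considered to be statistically significant unless otherwise specified".

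Protocol 12.6.1 names a different method for the two hospitalisation endpoints: "This rate will be compared between the AdreView™ and SoC groups using the Miettinen and Nurminen methodology", also with a margin of 1.20. It gives no significance level and no scale for the margin. SAP section 5 explains one change, that "country will be included in the model as the stratification factor instead of the enrolment site". It does not mention the change of method.

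**The concern.** An NI test needs a null placed at the margin. The CMH statistic is built under a common odds ratio of 1, so 1.20 appears nowhere in it. Read literally, the SAP states one hypothesis and names a test of another.

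The p-value could then be misread in either direction. If p < 0.05 in favour of AdreView is required, the NI question has become a superiority question. If p > 0.05 is taken as no worse, absence of evidence is reported as non-inferiority. The SAP does not say what result would count as non-inferior.

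**Working it through.** **Is there a plan figure to reproduce?** Not for these endpoints: the documents give no hospitalisation proportion, power or achieved sample size. As context, the primary event count can be checked. By the Schoenfeld formula, d = 4(1.960 + 0.842)² / [ln(0.84/1.20)]² = 31.40 / 0.1272 = 246.8, so 247 as stated. For the primary endpoint, then, 1.20 is properly used as a shifted null. The gap is confined to the two hospitalisation bullets.

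**Does any rule in the SAP fill the gap?**
- Default of two-sided p < 0.05 (section 5): applied to the CMH p-value, it tests OR = 1.
- Primary-analysis rule (5.4.2): reached by the Cox bullets through an explicit reference, which the hospitalisation bullets lack.
- Device-complication rule (5.4.3.1): superiority, not NI.

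**What difference does it make?** All counts below are assumed, as patients with at least one hospitalisation, AdreView vs SoC. With a single table,
- SE(ln OR) = √(1/a + 1/b + 1/c + 1/d)
- 95% limits = exp(ln OR ± 1.96 SE)
- one-sided NI p = Φ[(ln OR − ln 1.20)/SE], with ln 1.20 = 0.1823
- CMH without continuity correction.

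(a) 66/200 vs 60/200
- OR = (66 × 140)/(134 × 60) = 1.149; ln OR = 0.1391; SE = 0.2155
- 95% limits 0.753 to 1.753
- CMH p = 0.519
- NI p = Φ[(0.1391 − 0.1823)/0.2155] = Φ(−0.20) = 0.42. **NI not shown.**

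(b) 300/1000 vs 313/1000
- OR = (300 × 687)/(700 × 313) = 0.941; ln OR = −0.0612; SE = 0.0970
- 95% limits 0.778 to 1.138
- CMH p = 0.528
- NI p = Φ[(−0.0612 − 0.1823)/0.0970] = Φ(−2.51) = 0.006. **NI shown.**

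Splitting each example over three assumed countries, with Mantel-Haenszel estimates and Robins-Breslow-Greenland limits, gives the same limits and conclusions:
- (a) 33/100, 20/60, 13/40 vs 30/100, 18/60, 12/40: OR 1.149 (0.753 to 1.753), CMH p = 0.520.
- (b) 150/500, 90/300, 60/200 vs 156/500, 94/300, 63/200: OR 0.941 (0.778 to 1.138), CMH p = 0.529.

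**How often would each misreading go wrong?** This is a large-sample, unstratified approximation for assumed SoC proportions of 20% to 50%.

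| Patients per arm (assumed) | True OR 1.20: test of OR = 1 non-significant | True OR 1.00: test of OR = 1 significant in favour of AdreView | True OR 1.00: upper 95% limit < 1.20 |
|---|---|---|---|
| 200 | 85% to 88% | 2.5% | 11% to 15% |
| 500 | 70% to 78% | 2.5% | 21% to 30% |
| 1000 | 47% to 61% | 2.5% | 37% to 53% |

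At a true OR of 1.20 the upper-limit rule declares NI 2.5% of the time by construction. Taking non-significance as NI would be wrong at the rates in the second column. Demanding significance would almost never find NI when the groups are truly equal.

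**The case against.** The best defence is that the bullets are shorthand. Each names an effect measure (the odds ratio), a stratification factor, an NI objective and a margin, and nowhere does the SAP say that the CMH p-value decides NI. A programmer might well produce the Mantel-Haenszel odds ratio with a 95% interval and compare its upper limit with 1.20. Under the section 5 default a 95% interval is the natural one, and its upper limit is the one-sided 0.025 bound. This reading is plausible and may be what was meant, but it is not written down. The Cox bullets show that the authors could refer to the primary rule when they wanted it.

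It is also fair that the examples are illustrative. They change sample size and direction of effect together, and (b) has about as many patients as the full planned 2001, in a study that stopped early. They show that the p-value does not carry the NI answer; they do not measure an error in this trial.

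Several stronger readings are tempting but not supported:
- A reader might infer that the SAP supplies no significance level at all. It does have a default; what is missing is a rule tying it to the margin.
- A reader might infer that the margin was moved or loosened by adopting the odds ratio. The protocol (12.6.1, 12.9) names no scale, so no shift can be shown. If a risk ratio had been meant, OR 1.20 is the stricter choice: it corresponds to risk ratios of 1.18, 1.13 and 1.09 at assumed SoC proportions of 10%, 30% and 50%.
- A reader might infer a breach in the SAP's silence about leaving Miettinen-Nurminen. Protocol 12.13 asks for deviations and reasons in the final study report, which is not among the documents.
- A reader might infer that a confirmatory claim is at risk. SAP 5.4.4 rules that out: "All of the secondary endpoints will be analyzed inferentially as reference only".

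**Conclusion.** The point stands as a mismatch between hypothesis and test in two bullets. As written, the CMH test does not decide H0: OR ≥ 1.20, and neither the SAP default nor the primary-analysis rule is connected to these endpoints so as to repair that. This conclusion rests on the text and on what the CMH test is; it needs no assumed data.

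The impact is minor. The study ended early, hierarchical testing was dropped, and no claim depends on these endpoints. They will still be analysed inferentially under an NI label, so a reader of the report could draw an NI conclusion, and it should come from a rule that tests the margin. Its size in this trial cannot be stated, because the hospitalisation proportions and the achieved sample size are not in the documents.

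**What to change.** In both hospitalisation bullets of SAP 5.4.3.1:
1. Define the rate as the proportion of patients with at least one such hospitalisation, since an odds ratio needs a yes/no outcome per patient.
2. State H0: common OR (AdreView/SoC) ≥ 1.20 against Ha: OR < 1.20.
3. Estimate the country-stratified Mantel-Haenszel odds ratio with its two-sided 95% confidence interval, and conclude NI only if the upper limit is below 1.20 (one-sided 0.025).
4. Say that the CMH p-value is not used for NI.
5. Keep the reference-only label of 5.4.4.

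Record the change from the protocol's Miettinen-Nurminen method as a deviation, with its reason, in the study report under Protocol 12.13. A parallel Miettinen-Nurminen analysis is not needed: it would require choosing a scale that the protocol never gave and would add a second NI result for a reference-only endpoint.

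The cost is wording in two bullets and one deviation entry. The interval comes from the same country-by-arm tables as the CMH test, so no new data are needed.

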In addition to medical therapies, device therapies are available and have proven effectiveness, especially for improving HF symptoms and preventing sudden cardiac death (SCD). However, optimizing risk stratification and appropriately triaging individual patients to these invasive options to improve clinical outcomes remains a clinical challenge [Yancy et al. 2013] [Goldberger et al. 2011].

Present USA and European Union (EU) guidelines recommend implantation of an implantable cardioverter defibrillator device (ICD) in patients with left ventricular ejection fraction (LVEF) $\leq 35\%$ to reduce the risk of sudden death. Canadian guidelines [Bennett et al. 2017] further specify that additional risk assessment be performed in patients with LVEF values of 30% to 35% due to a lack of data supporting the use of prophylactic ICDs in this population.

Moreover, the recently-reported DANISH study has questioned the utility of prophylactic ICD therapy in patients with non-ischemic left ventricular dysfunction, possibly due to the lower risk of arrhythmic death with contemporary medical therapy. Further, only about half of all patients who meet the guideline-derived criteria actually have an ICD implanted reflecting the uncertainty of ICD benefit in patients with lesser degrees of left ventricular dysfunction. For example, in the first year after ICD implantation, as few as 5% of patients will actually experience a potentially fatal arrhythmia for which an ICD therapy is necessary [Moss et al. 2012]. Thus, the majority of patients who have an ICD implanted do not receive a survival benefit from it. These patients are not immune from the complications of device implantation and on-going care, including mechanical and infectious complications of the procedure, inappropriate device activation, device failure, and ultimately need for device replacement. Despite optimal therapy and device care, approximately 2% of patients with devices will die suddenly each year, and 3% will die from other cardiac causes, usually HF or myocardial infarction. Moreover, inappropriate shocks are associated with a higher incidence of all cause and cardiovascular death [Moss et al. 2012]. Ideally, only patients who will suffer a serious arrhythmia would have an ICD implanted. Yet, it is unlikely that this degree of risk stratification is attainable, given temporal changes in their underlying heart disease.

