12.9 Non-Inferiority Margin

The NI margin to be used for the analyses summarized in Sections 12.5.2 and 12.6.1 will be 1.20.

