2.3 Sample Size

The all-cause mortality rate that is expected in the study was estimated using the all-cause mortality rate observed in Study GE-122-016 at 36 months (internal report). It is assumed:

	Patients with $25\% \leq \text{LVEF} \leq 30\%$		Patients with $30\% \leq \text{LVEF} \leq 35\%$	
	%	Mortality Rate	%	Mortality Rate
H/M ratio <1.6	79%	20.25%	75%	15.14%
H/M ratio ≥ 1.6	21%	9.72%	25%	4.68%

In addition, the following observations or assumptions were taken: the ratio of patients with $25\% \leq \text{LVEF} \leq 30\%$ vs. $30\% \leq \text{LVEF} \leq 35\%$ is expected to be 1:4 to account for the prior enrollment of only patients with $30\% \leq \text{LVEF} \leq 35\%$; the hazard ratio of patients with ICD implantation vs. with usual care in the existing practice is 0.9 [Køber et al. 2016]. Referring to existing practice, only 15% of patients with $25\% \leq \text{LVEF} \leq 35\%$ currently receive ICD. Accordingly, the number of patients who currently do not receive ICD but who will receive it according to protocol and the number of patients who currently receive ICD and who will not receive it according to protocol have been calculated. In addition, the all-cause mortality rate of patients currently not receiving ICD but who will receive according to protocol (85% of patients with H/M ratio <1.6 in the AdreView™ group) has been corrected to take into account the 31% reduction in all-cause mortality observed at 20 months in the Multicentre Automatic Defibrillator Implant Trial (MADIT II) trial [Moss et al. 2012]. These assumptions led to a composite mortality rate of 11.34% in the AdreView™ group and 13.33% in the SoC group. The sample size was estimated with the hypothesis of not having a relative increase of mortality rate in excess of 20% in the AdreView™ group compared with the SoC group and with the following assumptions:

- Alpha = 0.025, 1-sided
- Statistical power = 80%
- 1:1 randomisation to AdreView™ and SoC groups
- $H_0: HR \geq HR_0$ vs. $H_1: HR < HR_0$. $HR_0 = 1.20$
- Assumed HR: 0.84
- Accrual time: 18 months
- The total study duration: 48 months
- AdreView™ group survival rate at 36 months: 0.887.

Based on the above assumptions, the required total number of events was 247, and the required total number of randomised patients was 2001. The planned study accrual was at least 2354 patients screened in order to randomise at least 2001 patients in the study.

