5.4.3.2 Additional Secondary Endpoints Analyses

- Syncope. The occurrence of this event will be analysed in the primary efficacy population using a Cox proportional hazards model as was performed in the primary efficacy analysis (NI, using an NI margin of 1.20). Patients who had not experienced syncope at the time of data base lock will be censored at the last known-alive date.
- Clinical and healthcare resource utilisation data collected in this study including ICD implantation, all hospitalisations, treatment of AEs, and AdreView™ administration will be used in an economic evaluation of study outcomes for relevant geographies. The clinical data may be summarised and compared between the AdreView™ and SoC groups. The healthcare resource utilization data will not be analysed due to early termination.
- A composite of the rate of hospitalisation and death related to major complications of device implantation (i.e., need for thoracotomy, pericardiocentesis, or vascular surgery) and a composite of the rate of complications of long-term device therapy (i.e., infection not leading to hospitalisation, lead and/or generator removal/replacement, inappropriate shocks, explantation). The occurrence of these events will be analysed using a Cox proportional hazards model as described in the primary efficacy analysis. These data will be analysed with a superiority analysis (HR of AdreView™ vs SoC < 1.0), using a 2-sided alpha value of 0.05. Kaplan-Meier plot will be presented by method of treatment guidance. Patients who had not experienced any of the events at the time of data base lock will be censored at the last known-alive date.
- The rate of ICD implantation and ICD explantation will be summarized for each study arm. In addition, the reasons of ICD implantation and ICD explantation will also be summarized. The odds ratio of the rate of ICD implantation and ICD explantation will be compared between the AdreView™ and SoC groups using the CMH test stratified by country.

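### The two hospitalisation non-inferiority comparisons have no rule for death, so a patient who dies without an admission counts as a non-event; each needs a death-inclusive companion analysis

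*SAP*

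**What the plan says.** SAP 5.4.3.1 gives the two hospitalisation endpoints, cardiovascular and all-cause, the same analysis: "The odds ratio of this rate will be compared between the AdreView™ and SoC groups using the CMH test stratified by country". Each has a non-inferiority margin of 1.20, in line with Protocol 12.9: "The NI margin to be used for the analyses summarized in Sections 12.5.2 and 12.6.1 will be 1.20". (Protocol 12.6.1 names a different method, Miettinen and Nurminen. It has no rule for death either.)

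No section of either document says how a death before any admission enters these two comparisons. There is no composite with death and no competing-risk method. SAP 5 leaves missing values unimputed.

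Syncope (SAP 5.4.3.2) is a Cox analysis: "Patients who had not experienced syncope at the time of data base lock will be censored at the last known-alive date". That covers patients who died without syncope.

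Sudden cardiac death is an event in three other analyses: all-cause mortality (SAP 5.4.2), cardiac death, and the arrhythmic composite (both SAP 5.4.3.1).

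Protocol 12.6 tested hospitalisation only after mortality, device harm and cardiac death had each succeeded. SAP 5.4.4 drops that order because of early termination: "All of the secondary endpoints will be analyzed inferentially as reference only".

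**The concern.** In an odds ratio of patients ever admitted, not admitted is the favourable category. A patient who dies at home with no earlier admission falls into it.

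In many trials this matters little. Here the arms differ by a device meant to prevent sudden death. AdreView-arm patients with H/M of 1.6 or more do not initially receive an ICD, and Protocol 6.4 accepts that a device of benefit may be withheld from some of them. The same arrhythmia could lead to a treated episode and an admission in an ICD carrier, and to an out-of-hospital death in a patient without one. The first counts against the patient's arm; the second does not.

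At stake is the reading of a hospitalisation non-inferiority result. It could be met partly because patients died, and the protocol's order of testing no longer stands in front of it. Rates per patient-year would not cure this, because the death itself would still not count.

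**Working it through.** **Inputs from the documents** (SAP 2.3, same figures in Protocol 12.8)
- LVEF 25–30% to 30–35% in the ratio 1:4, so weights 0.2 and 0.8.
- H/M of 1.6 or more: 21% and 25% of these groups, with 36-month mortality 9.72% and 4.68%.
- ICD effects: hazard ratio 0.9, and a 31% mortality reduction.
- 36-month mortality 11.34% (AdreView) and 13.33% (SoC); assumed hazard ratio 0.84; margin 1.20; 247 events.

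**The plan's figures reproduce**
- Events: 4 × (1.960 + 0.842)² / [ln(0.84/1.20)]² = 246.8, so 247.
- Hazard ratio: ln(1 − 0.1134) / ln(1 − 0.1333) = 0.841.
- Low-risk share: 0.2 × 21% + 0.8 × 25% = 24.2% (the plan uses 24%).

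**Step 1. Low-risk deaths per 1000 randomised to an arm**

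1000 × (0.2 × 0.21 × 0.0972 + 0.8 × 0.25 × 0.0468) = 13.4, which is 5.55% of the low-risk group.

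**Step 2. Extra deaths if withholding the ICD forgoes its benefit**

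Assumptions: the plan's two ICD effects apply to the low-risk group, and 13.4 is the figure with an ICD.
- Hazard ratio 0.9: 13.4 × (1/0.9 − 1) = 1.5.
- 31% reduction: 13.4 × (1/0.69 − 1) = 6.0.

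If 13.4 is instead the figure without an ICD, the extra deaths are 13.4 × 0.10 = 1.3 and 13.4 × 0.31 = 4.2, so 1.5–6 is the wider case.

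**Step 3. Shift in the hospitalisation odds ratio**

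The documents give no admission rate. Assume p = 30% ever admitted (range 20–40%), no true effect on admission, and all k extra deaths (per 1000) occurring before any admission. Let f be the share of these patients who would otherwise have been admitted. Country strata are ignored.

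OR = odds(p − kf/1000) / odds(p); share of log margin = −ln(OR) / ln(1.20)

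| p | f | OR, k = 1.5 | OR, k = 6 | Share of log margin |
|---|---|---|---|---|
| 30% | all | 0.993 | 0.972 | 4–16% |
| 30% | average (30%) | 0.998 | 0.991 | 1–5% |
| 20% | all | 0.991 | 0.963 | 5–21% |
| 40% | all | 0.994 | 0.975 | 3–14% |

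For example, p = 30%, k = 6, f = all: (0.294/0.706) / (0.300/0.700) = 0.972. If none would have been admitted (f = 0), the OR stays at 1.00. These shifts do not depend on the number of patients.

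**Step 4. Direction under the plan's mortality assumption**

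Use constant hazards over 3 years: death in SoC −ln(1 − 0.1333)/3 = 0.0477 per year, and first admission 0.15 per year in both arms (assumption). The proportion admitted is s/(s + h) × [1 − exp(−3(s + h))], where s is the admission hazard and h the death hazard. It is 0.3395 in SoC.
- Death hazard ratio 0.84: 0.3430, OR 1.016 (a simulation with shared frailty gives 1.014). The bias is against AdreView.
- Death hazard ratio 1.2: 0.3351, OR 0.98. The bias favours AdreView.

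**Step 5. What a death-inclusive version changes**

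Illustration: 1000 per arm, p = 30%, 3% of each arm dying without admission, 5 extra AdreView deaths, average admission risk.
- Hospitalisation alone: 29.85% against 30%, OR 0.993, chance of meeting 1.20 about 49%.
- Hospitalisation or death: 33.35% against 33%, OR 1.016, chance about 42%.

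**The case against.** The strongest case on the other side has four parts.

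**The harm is tested elsewhere.** A sudden death after a withheld ICD counts against AdreView in the primary endpoint, in cardiac death and in the arrhythmic composite. This stands, and it limits the importance of the gap. It does not repair the two hospitalisation comparisons, which are still reported against a margin.

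**Nothing confirmatory is at stake.** SAP 5.4.4 makes all secondary endpoints reference only. This also stands: a reader might infer that a sudden death helps the AdreView arm pass, but the SAP has no formal pass to gain, and under the protocol's hierarchy mortality and cardiac death came first. What remains is that the 1.20 margin is kept, so a favourable hospitalisation result can appear beside an inconclusive mortality result.

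**The direction is not fixed.** The sample size assumes fewer AdreView deaths, and then the omission works against AdreView. That assumption uses 15% ICD use in existing practice, whereas Protocol 6.1 and 9.3 have SoC patients undergoing implantation, so the documents do not settle the direction. Low-risk patients may also receive an ICD later (Protocol 9.4 and 9.5), which would reduce the effect.

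**Large effects need inputs the plan does not support.** It is tempting to use Protocol Section 4's "as few as 5% of patients will actually experience a potentially fatal arrhythmia for which an ICD therapy is necessary" as the rate of lost lives. That figure describes ICD recipients in general in their first year, not patients with H/M of 1.6 or more, and it is not a rate of certain death without a device. Applied to 240 low-risk patients per 1000, it would add 12 deaths to the plan's 13.4 and nearly double their mortality.

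A reader might also infer that syncope rewards death in the same way. It does not. Censoring removes the patient from the risk set rather than scoring a good outcome. In simulation the syncope hazard ratio stayed at about 1.00 when syncope and death were independent. With shared frailty it fell to 0.98–0.99 (death hazard ratio 1.2) or 0.94–0.97 (death hazard ratio 1.5).

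**Conclusion.** The point holds for the two hospitalisation endpoints. The SAP leaves death before admission unaddressed, and the chosen statistic makes it a non-event. The arm with more such deaths is favoured.

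The size is modest on the plan's own figures, and it depends mainly on how many of the patients who died would otherwise have been admitted, which the documents do not tell us. All-admitted is the upper limit for any given number of extra deaths. The estimate also rests on an assumed admission proportion and on applying the plan's ICD effects to the low-risk group.

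This is a source of bias of uncertain sign that is cheap to make visible. It does not show that the plan credits harm to AdreView, and it does not justify replacing the protocol's key secondary endpoints. For syncope, a bias arises only if those who die had a higher risk of syncope.

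**What to change.** In SAP 5.4.3.1, keep both hospitalisation endpoints as they are and:
1. State that a patient who dies without an admission is counted as not admitted.
2. Add two time-to-first-event Cox models, stratified as in SAP 5.4.2: cardiovascular hospitalisation or cardiovascular death, and all-cause hospitalisation or death. Show the hazard ratio and its 95% interval against 1.20.
3. Tabulate by arm the deaths with no prior admission, for each hospitalisation endpoint.
4. State that a hospitalisation non-inferiority result is interpreted only beside its death-inclusive version.

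For syncope (SAP 5.4.3.2), a death-inclusive sensitivity analysis is optional, since the arrhythmic composite already counts sudden cardiac death.

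The cost is SAP text, two models and a table, from deaths and admissions the study already records (dates of first admission are assumed to be on file). There are two downsides. The composites partly repeat the mortality result. And SAP 3.1.3 leaves all-cause hospitalisation out of adjudication, so that component would rest on site reports; cardiovascular hospitalisation and cardiac death, which includes other cardiovascular causes, are adjudicated.
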